9.3. Other Secondary Efficacy Endpoints

The following secondary efficacy endpoints will be assessed up to Day 14 and up to Day 28, unless otherwise specified:

- Proportion of patients requiring supplemental oxygen due to SARS-CoV-2 infection (after study drug administration)
- Proportion of patients with intensive care unit transfer due to SARS-CoV-2 infection (after study drug administration)
- Proportion of patients with all-cause mortality (after study drug administration)
- Time to clinical recovery (after study drug administration)
- Duration of fever defined as the last day in the patient diary on which the temperature >38 °C (100.4 °F) is recorded, or a potentially antipyretic drug (acetaminophen or ibuprofen) is taken.
 - Duration of fever will be calculated for patients with the temperature >38 °C (100.4 °F) or a potentially antipyretic drug on or before study drug administration.
 - A potential antipyretic drug (including but not limited to acetaminophen, paracetamol or ibuprofen) will be identified by medical review.

- Proportion of patients with hospital admission due to SARS-CoV-2 infection (after study drug administration)
- Proportion of patients with mechanical ventilation due to SARS-CoV-2 infection (after study drug administration)
- Proportion of patients requiring rescue therapy due to SARS-CoV-2 infection (after study drug administration)
 - Rescue therapy is defined as prohibited therapy on or after the study drug administration on Day 1.
 - A prohibited therapy due to SARS-CoV-2 infection (including but not limited to remdesivir, chloroquine, hydroxychloroquine, dexamethasone [alternative corticosteroids to dexamethasone], interferon beta-1b, ribavirin, lopinavir-ritonavir, human intravenous immunoglobulin, convalescent plasma, tocilizumab, sarilumab, SARS-CoV-2 vaccine) will be identified by medical review before unblinding.
- Proportion of patient with negative conversion in nasopharyngeal swab specimen based on RT-qPCR at each visit (after study drug administration)
 - Patients who have negative result for at least two consecutive time points will be considered as satisfying negative conversion at the first time point. The two consecutive time points will be determined excluding missing data. If patients who have one negative result followed by all missing results will also be considered as satisfying negative conversion.
- Time to negative conversion in nasopharyngeal swab specimen based on RT-qPCR (after study drug administration)
 - Time to negative conversion in nasopharyngeal swab specimen based on RT-qPCR will be calculated as (Date/time of event or censoring – Date/time of study drug administration)
- Time to National Early Warning Score 2 (NEWS2) of 0 (after study drug administration)
 - Patients whose sum of each parameter score meet 0 will be considered as satisfying NEWS2 of 0.
 - Time to NEWS2 of 0 will be calculated as (Date of event or censoring – Date of study drug administration).
- Scores of other known SARS-CoV-2 Infection symptoms such as vomiting, diarrhea, loss of taste or smell at each visit

The secondary efficacy endpoints listed in this section will be analyzed on both ITT and ITTI sets. Confidence interval and p-value will be presented for comparison between treatment groups in a descriptive manner with no adjustments for multiple testing.

Binary endpoints and time to event endpoints will be summarized and analyzed using the same statistical method as the key secondary endpoints ([Section 9.2](#)). For time to event endpoint, time to event will be defined as the elapsed time (in days) from the study drug administration to the earliest day satisfying condition for event. The same censoring rules used for clinical recovery of the key secondary endpoints ([Section 9.2](#)) will be applied.

Continuous endpoints will be summarized using descriptive statistics and analyzed using Analysis of Covariance (ANCOVA) presenting a point estimate, p-value and 95% CI for the treatment difference. Covariates for ANCOVA will include stratification factors used for the primary analysis.

For analysis of time to event endpoints, the following patients will be included in the analysis set:

- Time to clinical recovery: Patients who report at least one symptom at baseline
- Time to negative conversion: Patients who have positive result confirmed based on the negative threshold (as defined in [Section 11.1.1](#)) in the analysis at baseline (or Day 2/Day 3). The same analysis set will be used for the proportion of negative conversion.
- Time to NEWS2 of 0: Patients who have NEWS2 > 0 at baseline

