5.4. Analysis Sets

The following patient analysis sets are defined: Intent-to-Treat (ITT) Set, ITT Set – High Risk, Intent-to-Treat Infected (ITTI) Set, ITTI Set – High Risk and Safety Set.

Analysis of the ITT Set, ITT Set – High Risk, ITTI Set and ITTI Set – High Risk will be performed according to the treatment they were randomized to. The Safety Set will be analyzed according to actual treatment group. The actual treatment group will be assigned according to their actual treatment, not according to the randomized group, even if there is a discrepancy between the actual treatment administered and the randomized group.

For analysis of time to event endpoints, the following patients will be included in the analysis set:

- Time to clinical recovery: Patients who report at least one symptom at baseline
- Time to negative conversion: Patients who have positive result confirmed based on the negative threshold (as defined in [Section 11.1.1](#)) in the analysis at baseline (or Day 2/Day 3). The same analysis set will be used for the proportion of negative conversion.
- Time to NEWS2 of 0: Patients who have NEWS2 > 0 at baseline

The number of patients in each analysis set will be tabulated by the treatment group. A listing will also be produced displaying data on ITT Set, unless otherwise specified.

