7. DEMOGRAPHICS, BASELINE, AND BACKGROUND CHARACTERISTICS

7.1. Demographics and Stratification Details

The following demographic measures will be summarized for the ITT Set and ITT Set – High Risk by treatment group: Age (years); Sex (Male, Female); Female fertility status (Pre-Menarche, Surgically Sterilized, Post-Menopausal, Potentially Able to Bear Children); Race (White, Black or African American, American Indian or Alaska Native, Asian, Native Hawaiian or Other Pacific Islander, Not Allowed by Investigator Country Regulations, Other); Ethnicity (Hispanic or Latino, Non-Hispanic or Non-Latino, Unknown); Height (cm), Weight (kg) and BMI (kg/m^2) as recorded at the screening visit.

Age will be automatically calculated in the eCRF system based on the date of the informed consent visit and the year of birth considering whether birth date has passed the informed consent date or not.

The following stratification details will also be summarized for the ITT Set and ITT Set – High Risk by treatment group: age (≥ 60 years vs. < 60 years), baseline comorbidities (Yes vs. No, having at least one of cardiovascular disease, chronic respiratory disease, hypertension, diabetes mellitus, and pneumonia) and region (United States vs. Asia vs. European Union vs. other) for Part 2. If there is a difference for data entered between IWRS and eCRF, the stratification factors will be summarized using the final data collected on the eCRF.

The following Baseline characteristics will also be summarized for the ITT Set and ITT Set – High Risk by treatment group: high-risk status (Yes vs. No); screening obesity ($\text{BMI} > 30 \text{ kg}/\text{m}^2$ vs. $\text{BMI} \leq 30 \text{ kg}/\text{m}^2$); screening disease severity (Mild vs. Moderate); baseline viral load titer ($\log_{10}\text{cp}/\text{mL}$; negative titer threshold: $2.33 \log_{10}\text{cp}/\text{mL}$); day1 serostatus (Sero Positive, Sero Negative and Other);

Baseline characteristics will be defined as follows:

- Screening disease severity (Mild vs. Moderate):
 - A patient will be considered to have mild disease severity if the question “Are there any radiological findings of pneumonia and clinical signs of pneumonia?” is answered ‘No’ on the ‘Radiography’ page of eCRF at the screening visit.

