group. For the comparison between treatment groups, the primary efficacy endpoint will be tested at the 2-sided significance level of 5% on the ITT set – High Risk using Cochran-Mantel-Haenszel (CMH) test stratified by age (≥ 60 years vs. < 60 years), baseline comorbidities (Yes vs. No) and region (United States vs. European Union vs. other). For the region, the patients in Asia are included in other category as the number of patients in Asia was confirmed to be around 1% during blinded DRM. The difference of proportions between two treatment groups estimated using CMH weights will also be provided along with the 95% stratified Newcombe CI with CMH weights. Supportive analysis will be performed on ITTI set – High Risk using the same analysis method for the primary efficacy analysis. For sensitivity analysis, Fisher's exact test will be conducted on ITT set – High Risk. The 95% exact CI (Chan and Zhang 1999) for the treatment difference will also be provided. Additionally, sensitivity analysis will be performed for the primary analysis excluding 7 patients randomized in site 6179 which terminated its participation in the study by Institutional Review Board (IRB)'s decision due to serious and continuing non-compliance to the protocol and GCP.

In addition, the analysis for the following subgroups will be conducted on ITT set – High Risk:

- Age (< 60 years, ≥ 60 years, ≥ 50 years)
- Baseline comorbidities (Yes, No)
- Region (United States, Asia, European Union, Other)
- Race (White, Black or African American, American Indian or Alaska Native, Asian, Native Hawaiian or Other Pacific Islander, Not Allowed by Investigator Country Regulations, Other)
- Sex (Male, Female)

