9.2. Key Secondary Efficacy Analysis

If the primary endpoint is statistically significant, the key secondary endpoints will be tested using the fixed sequence procedure in order to preserve the Type I error. The order of testing is as follows:

- Proportion of patients with clinical symptom requiring hospitalization, oxygen therapy, or experiencing mortality due to SARS-CoV-2 infection up to Day 28 in all randomized patients.
- Time to clinical recovery up to Day 14 in high-risk patients.
- Time to clinical recovery up to Day 14 in all randomized patients.

The first key secondary endpoint will be tested only if the primary endpoint is statistically significant, and the next key secondary endpoint will be tested only if the previous key secondary endpoint is statistically significant.

The key secondary endpoints will be tested at the 2-sided significance level of 5% on the ITT set (for high-risk patients, ITT set - High Risk) using the p-value from stratified CMH

test for binary endpoint or stratified log-rank test for time to event endpoints. The same stratified analysis used for the primary endpoint analysis will be applied.

The supportive analysis will be performed on ITTI set (for high-risk patients, ITTI set - High Risk). Additionally, sensitivity analysis will be performed for the key secondary analysis excluding 7 patients randomized in site 6179 which terminated its participation in the study by IRB's decision due to serious and continuing non-compliance to the protocol and GCP.

Binary endpoint (the first key secondary endpoint) will be summarized using frequency table along with 95% Wilson (score) CI for each proportion of treatment, and difference of proportions between two treatment groups estimated using CMH weights and corresponding 95% stratified Newcombe CI with CMH weights will be presented along with p-value from stratified CMH test.

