For time to event endpoints (the second and third key secondary endpoints), Kaplan-Meier methodology will be used to estimate the 25th percentile, 50th percentile (median) and 75th percentile in each treatment arm. The Brookmeyer-Crowley methodology (via log-log transformation) will be used to construct the 95% CI for each percentile. The treatment difference will be assessed by the stratified log-rank test presenting p-value. Hazard ratio between two treatment groups and associated 95% CI will be estimated using the stratified Cox proportional hazard model. Since clinical recovery is beneficial outcome, not hazard, the hazard ratio will be expressed as recovery rate ratio.

For time to clinical recovery endpoints, patients who report at least one symptom at baseline will be included in the analysis.

Clinical recovery is defined as all symptoms on the SARS-CoV-2 Infection Symptom Checklist 1 being recorded as 'absent' or 'mild' in intensity for both at least 48 hours. To meet the clinical recovery, all symptoms of SARS-CoV-2 Infection Symptom Checklist 1 defined in [Table 2](#) should satisfy one of the following conditions.

- ✓ Symptoms 'severe' or 'moderate' in intensity at baseline should be changed to 'mild' or 'absent' after the study drug administration for at least 48 hours.
- ✓ Symptoms 'mild' in intensity at baseline should be changed to 'absent' after the study drug administration for at least 48 hours.
- ✓ Symptoms 'absent' in intensity at baseline should maintain as 'absent' for at least 48 hours.
- ✓ Symptoms 'absent' in intensity at baseline becomes 'severe', 'moderate', or 'mild' during the study and changes back to 'absent' for at least 48 hours.
- ✓ Missing symptoms at baseline becomes 'absent' for at least 48 hours.

Patients who meet the clinical recovery criteria for at least two consecutive time points at each symptom will be considered as satisfying condition of 48 hours and achieving clinical

recovery at the first time point. The checklist at Screening or on Day 1 will be used to determine baseline and checklist from Day 2 will be used to determine clinical recovery. If the checklist from Day 2 is recorded twice a day, evening diary will be used to determine clinical recovery. From Day 2, missing time in SARS-CoV-2 Infection Symptom Checklist 1 will be imputed as 10PM for calculation of time to recovery.

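### Time to negative conversion (and time to NEWS2 of 0) is analysed without the endpoint's own pre-dose value, which gives up efficiency that data already collected could recover

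*SAP*

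**What the plan says.** - **Method.** SAP 9.3: "Binary endpoints and time to event endpoints will be summarized and analyzed using the same statistical method as the key secondary endpoints". SAP 9.2 supplies that method: "The treatment difference will be assessed by the stratified log-rank test presenting p-value", and "Hazard ratio between two treatment groups and associated 95% CI will be estimated using the stratified Cox proportional hazard model". No covariate is named. Protocol 7.8.3.3 specifies the same test and model for Part 2.
- **Strata.** SAP 9.2: "The same stratified analysis used for the primary endpoint analysis will be applied". In SAP 9.1 the primary test is "stratified by age (≥ 60 years vs. < 60 years), baseline comorbidities (Yes vs. No) and region (United States vs. European Union vs. other".
- **Covariates elsewhere in SAP 9.3.** Only continuous endpoints have a covariate sentence: "Covariates for ANCOVA will include stratification factors used for the primary analysis". It does not name the baseline value either.
- **Targets.** Negative conversion means RT-qPCR results below a threshold, with 2.33 log10 cp/mL as the main one and 3 and 4 as additional ones (SAP 11.1.1). The NEWS2 event is a total score of 0 (SAP 9.3).
- **Starting levels.** SAP 5.4 admits "Time to NEWS2 of 0: Patients who have NEWS2 > 0 at baseline". For negative conversion it admits patients positive at baseline or, failing that, at Day 2 or Day 3.
- **Availability.** The swab and NEWS2 are both scheduled pre-dose on Day 1 (SAP Appendix 1). SAP 7.1 already tabulates "baseline viral load titer" as a baseline characteristic.
- **Status.** SAP 9.3 presents the intervals and p-values descriptively, with no multiplicity adjustment.

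**The concern.** Both endpoints measure how long a patient takes to fall to a fixed level from whatever level he or she started at. The distance to fall is close to part of the endpoint's definition, and age, comorbidity and region are at best indirect proxies for it. Leaving a prognostic baseline value out of a time-to-event comparison has two known effects. The test has less power, and the estimated ratio sits nearer 1 than the ratio between patients with the same baseline.

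What is at stake is the precision of Part 2's between-group virology comparison. The viral shedding summaries in SAP 11.1.1 are descriptive by arm, so the comparisons that carry a p-value and interval are negative conversion as a proportion and as a time to event.

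**Working it through.** **1. The plan's own figures.** Neither document states power for these two endpoints. The nearest figure is time to clinical recovery up to Day 14, which uses the same test. With d events, ratio R, 1:1 allocation and two-sided 5%, power = Φ(√(d/4) × ln R − 1.96).

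- All randomized: d = 1300 × 0.90 × 0.65 = 760.5 and R = 1.35. √190.1 × 0.300 − 1.96 = 2.18, so power is 98.5%.
- High-risk: d = 822 × 0.90 × 0.66 = 488.3 and R = 1.5. √122.1 × 0.405 − 1.96 = 2.52, so power is 99.4%.

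Both agree with the stated minimum of 90%.

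**2. Inputs that must be assumed.** The documents give no spread of baseline viral load or NEWS2, no prognostic strength, and no expected ratio for these endpoints. The simulations use N = 1300 × 0.90 = 1170, 1:1, two-sided 5% and 1000 runs per setting. The 90% is borrowed from clinical recovery, where it is the share with baseline symptoms; the RT-qPCR-positive share is not given. The planned analysis is represented by an unadjusted Cox fit, since the log-rank test is that model's score test.

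**3. Model A: proportional hazards.** 65% of patients have the event by Day 14, the ratio at a given baseline is 1.2, and a standardised baseline value changes the log hazard by g per SD.

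| g | Power without → with baseline | Gain (points) | Ratio without → with |
|---|---|---|---|
| 0 | 71.0% → 71.5% | 0.5 | 1.20 → 1.20 |
| 0.3 | 66.7% → 71.4% | 4.7 | 1.195 → 1.203 |
| 0.5 | 61.3% → 70.1% | 8.8 | 1.178 → 1.198 |
| 0.8 | 52.2% → 71.9% | 19.7 | 1.156 → 1.202 |
| 1.0 | 49.0% → 72.7% | 23.7 | 1.148 → 1.205 |

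Check on the g = 0 row: √(760/4) × ln 1.2 − 1.96 = 0.55, which gives 71.0% by formula.

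A separate run with 60% events and a ratio of 1.25 gave 80.4% → 84.0%, 77.1% → 86.7% and 63.9% → 83.7% at g = 0.3, 0.5 and 0.8. The unadjusted ratios were 1.24, 1.23 and 1.20.

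**4. Model B: viral decline.** Log10 viral load falls linearly to 2.33 and is read at the Part 2 swab days up to Day 14. Assumed: baseline mean 6; decline 0.30 per day, varying between patients on the log scale; decline 10% faster on drug.

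| Baseline SD | Decline log-SD | Power without → with | Gain (points) | Ratio without → with |
|---|---|---|---|---|
| 1 | 0.4 | 73.8% → 87.3% | 13.5 | 1.203 → 1.238 |
| 1.5 | 0.4 | 57.3% → 82.0% | 24.7 | 1.172 → 1.227 |
| 2 | 0.4 | 42.0% → 75.6% | 33.6 | 1.143 → 1.211 |
| 1 | 0.8 | 31.0% → 33.4% | 2.4 | 1.125 → 1.132 |
| 1.5 | 0.8 | 26.6% → 30.2% | 3.6 | 1.109 → 1.123 |
| 2 | 0.8 | 18.7% → 24.5% | 5.8 | 1.095 → 1.114 |

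**5. No treatment effect.** The unadjusted analysis rejected in 4.1% of runs (Model A, g = 0.8) and 2.3% (Model B, baseline SD 1.5, log-SD 0.4), with ratios of 1.00. Type I error is not inflated. Model B's low rate fits its heavily tied event times and Breslow tie handling, which affect both columns.

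**6. Not modelled.** The planned strata, the rule of two consecutive negatives, censoring for rescue therapy or hospitalisation, patients entering at Day 2 or Day 3, and NEWS2 itself.

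**The case against.** - **No decision rests on these p-values.** They are descriptive, outside the fixed sequence, and have no power target. This stands. A reader might infer that the primary or key secondary results are weakened; they are not, because neither endpoint feeds them.
- **Attenuation is not bias.** A reader might infer that the planned ratio wrongly understates the antiviral effect. In a randomized comparison the unadjusted ratio validly estimates a marginal quantity. It differs from the baseline-conditional ratio because the hazard ratio is non-collapsible, so the two answer different questions. The efficiency argument survives; a claim of bias does not.
- **The size is assumed.** Model A makes the adjusted analysis correct by construction. In Model B, when decline rates vary widely between patients, the gain is only about 2 to 6 points. No single power figure can be claimed.
- **NEWS2 was not examined.** Eligibility requires SpO2 above 94% without oxygen, which limits the Scale 1 SpO2 item to 0 or 1 and the oxygen item to 0. A respiratory rate of 30 or more is excluded. Other items can still vary, so the direction of the argument carries over, but the viral-load figures do not.
- **Late-positive patients.** A Day 1 negative who turns positive at Day 2 or Day 3 has a rising viral load. Under SAP Table 5 that patient's pre-dose value becomes 2.33, which a linear term would read as closest to clearance. This is a real defect of simple adjustment, and the change must handle it.
- **Other virology summaries exist.** Change from baseline, viral AUC and shedding duration are planned, and change from baseline does use the starting value. They are summarised descriptively and do not replace this comparison.

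**Conclusion.** The omission is confirmed from the text: neither document puts baseline viral load or baseline NEWS2 into the test or model for its own endpoint. The consequence is lost efficiency on two descriptive secondary endpoints. For viral load, adjustment raised power by about 2 to 34 points across the settings in which baseline was prognostic, and it cost nothing measurable where baseline had no effect (71.0% against 71.5%). That range rests on assumed spreads, decline rates and effects, because the documents supply none. For NEWS2 only the direction can be argued. Type I error, the validity of the planned marginal ratio, and the primary and key secondary conclusions are all unaffected. The change is worth making because it is nearly free; the trial's main claims do not depend on it.

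**What to change.** Settle this before unblinding, so that the choice cannot look selective.

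1. In SAP 9.3, add pre-dose log10 viral load as a continuous covariate to the stratified Cox model for time to negative conversion.
2. Add a separate indicator for patients whose Day 1 result is negative or missing and who enter through a Day 2 or Day 3 positive, so that 2.33 is not read as an ordinary low value for them.
3. Report the covariate-adjusted rate ratio, 95% CI and p-value. Show the protocol's stratified log-rank test and the unadjusted ratio alongside.
4. Optionally, add baseline NEWS2 to the model for time to NEWS2 of 0. Entry requires a baseline score above 0, so every analysed patient has the covariate. State that the gain is unquantified.
5. Record the change in SAP Section 12, since it departs from the log-rank p-value stated in Protocol 7.8.3.3.

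The cost is a few lines of SAP text and one or two extra terms per model, with no new data. The downsides are that the adjusted ratio is conditional on baseline and must be labelled so, and that a descriptive endpoint moves away from the protocol's stated p-value. Reporting both analyses covers each.

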Time to clinical recovery is defined as the elapsed time (in days) from the study drug administration to the earliest day satisfying condition for clinical recovery, and calculated as (Date/time of event or censoring – Date/time of study drug administration). The following patients will be considered censored at their scheduled visit of interest (Day 14).

- Patients who are ongoing in the study without event
- Patients with death or early withdrawal for any reason prior to their scheduled visit of interest (Day 14)
- Patients who administered the rescue therapy due to SARS Cov-2 infection (as defined in [Section 9.3](#)) prior to their scheduled visit of interest (Day 14)
- Patients who were hospitalized due to SARS-CoV-2 infection (as defined in [Section 9.1](#)) prior to their scheduled visit of interest (Day 14)

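### Time to negative conversion borrows the symptom-recovery censoring rule, so a hospitalized or rescued patient whose swabs show conversion is scored as unconverted, which tilts this descriptive comparison toward the arm with fewer such events

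*SAP*

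**What the plan says.** SAP 9.3 defines conversion from swabs alone: "Patients who have negative result for at least two consecutive time points will be considered as satisfying negative conversion at the first time point". A single negative followed only by missing results also counts. For the time-to-event version it adds that "The same censoring rules used for clinical recovery of the key secondary endpoints" will be applied, without exempting this endpoint.

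The rules in SAP 9.2 list four groups to be censored at the scheduled visit of interest, given there as Day 14:

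- "Patients who are ongoing in the study without event"
- patients who die or withdraw early
- patients given rescue therapy for SARS-CoV-2 before that visit
- "Patients who were hospitalized due to SARS-CoV-2 infection" before that visit, using the SAP 9.1 definition

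Only the first group is conditioned on having had no event.

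On the horizon, SAP 9.3 states: "The following secondary efficacy endpoints will be assessed up to Day 14 and up to Day 28, unless otherwise specified". These endpoints are analyzed on the ITT and ITTI sets, with p-values presented descriptively and no multiplicity adjustment. SAP 9.3 also says that the proportion with negative conversion uses the same analysis set as the time-to-event version. No hospitalization or rescue rule is attached to the proportion.

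**The concern.** The rule was written for a diary-based symptom endpoint. Protocol 6.1.1 lets diary recording stop when the patient cannot record, for example under sedation, so hospitalization can interrupt that measurement. Conversion is a laboratory result, and the protocol states no corresponding stop for swabs.

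Censoring is at the horizon, not at the date of hospitalization or rescue. An affected patient therefore stays in the risk set throughout as someone who never converts. If these events are more frequent on placebo, more placebo conversions are removed. A purely clinical effect of CT-P59 would then show up as faster viral clearance, and two endpoints built from the same swabs could disagree.

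**Working it through.** **1. Two patients under the two endpoints.** Part 2 swabs are scheduled on Days 1, 3, 7, 10, 14, 21 and 28 (Protocol Table 6-3). Both patients are positive at baseline.

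- Hospitalized on Day 5, negative on Days 7, 10 and 14. Proportion endpoint: converted, dated Day 7. Time-to-event endpoint: unconverted to Day 14.
- Negative on Days 3 and 7, hospitalized on Day 9. Proportion endpoint: converted, dated Day 3. Time-to-event endpoint, read literally: unconverted to Day 14, although conversion came before the hospitalization.

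**2. Input rates.** The documents give no figure for time to negative conversion and no separate hospitalization or rescue rate. The nearest is the all-randomized composite of hospitalization, oxygen therapy or death up to Day 28 in SAP 5.2: 5.5% on placebo and 2.5% on CT-P59, with 650 per group. As a check on these inputs, the usual two-proportion normal approximation gives power of 0.789, against the at least 80% stated there.

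**3. Effect on the Kaplan-Meier estimate.** Every patient without a counted event is censored at the horizon, so nobody leaves the risk set early. The estimate of conversion at the horizon is then events divided by patients. Let *h* be the share hospitalized and *c* the share of those who would otherwise count as converted, assumed equal in both arms. The rule lowers an arm's estimate by *h* × *c*, so the spurious difference is (h placebo − h CT-P59) × *c*.

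- Patients affected: 650 × 0.055 = 35.75 on placebo; 650 × 0.025 = 16.25 on CT-P59. These counts are upper bounds, because only patients with confirmed positive swabs enter the analysis.
- Gap: 5.5 − 2.5 = 3.0 points.
- With *c* = 0.25 (assumption): 3.0 × 0.25 = 0.75 points.
- With *c* = 0.75 (assumption): 3.0 × 0.75 = 2.25 points.

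**4. Effect on the rate ratio and log-rank test.** This was simulated on the Part 2 swab days with no true viral effect, conversion independent of hospitalization, 90% of patients positive at baseline (585 per arm), the rates in step 2, and 1000 to 2000 runs per row. The conversion percentages and the 90% are assumptions. Each cell shows the rate ratio and the two-sided rejection at 5%.

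| Converting, both arms | SAP rule | Conversions before hospitalization counted | All swabs counted |
|---|---|---|---|
| 30% by Day 14 | 1.04, 6.6% | 1.02, 4.4% | 1.00, 4.6% |
| 50% by Day 14 | 1.05, 7.4% | 1.03, 6.6% | 1.00, 4.2% |
| 70% by Day 14 | 1.06, 12.6% | 1.03, 6.8% | 1.00, 5.6% |
| 90% by Day 28 | 1.09, 20% | 1.05, 11% | 1.00, 5.4% |

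Simulation error near 5% is about 0.5 to 0.7 points, so the first two rows under the SAP rule are only slightly above nominal. With equal event rates (4% in each arm) the rule gives a ratio of 1.00 and about 5% rejection: the bias needs unequal rates. If hospitalized patients clear virus at half the rate, the rule gives 1.04–1.09 and counting all swabs gives 1.02–1.03.

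**5. Horizon.** The rates in steps 3 and 4 run to Day 28. For the Day 14 estimate only hospitalization or rescue before Day 14 triggers the rule, so the Day 14 figures are on the high side for hospitalization.

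**The case against.** The best defence is that this is an unstated but reasonable composite strategy. Rescue therapy includes drugs that may lower viral load, such as remdesivir, convalescent plasma and immunoglobulin. Hospitalization under SAP 9.1 is not mere admission: it needs at least 24 hours of acute care plus treatment such as qualifying oxygen, remdesivir or tocilizumab. The last two are also on the rescue list. Counting swabs regardless would credit drug-assisted clearance as conversion, more often in the arm with more rescue, and so could bias the other way.

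That stands as a reason for a sensitivity analysis. It does not carry the rule as the main analysis. A conversion documented before rescue cannot be due to it. A hospitalization can qualify on oxygen alone. The rescue list also contains SARS-CoV-2 vaccine. The SAP names no such strategy, and its section 12 on changes in the planned analysis gives no rationale.

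Two more points stand. Swabs are taken by trained site personnel and the protocol excludes only anticipated transfer to a non-study hospital, so swabs after admission are scheduled but not assured. And observed virology stays visible elsewhere: the proportion converted, and the viral load, shedding duration and AUC summaries in SAP 11.1.1, do not use this rule.

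A reader might apply the high-risk rates (7.1% vs 2.9%) and infer a gap of 4.2 × 0.25 to 4.2 × 0.75, about 1.1 to 3.2 points. The documents do not support this: SAP 9.3 plans these endpoints on the ITT and ITTI sets only, and the high-risk sets are named for the primary and key secondary analyses. A reader might also infer a threat to the trial's controlled type I error. There is none, because the endpoint lies outside the fixed sequence.

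**Conclusion.** The concern holds for one descriptive endpoint. Read literally, the SAP overrides documented conversion in hospitalized or rescued patients and conflicts with its own proportion endpoint. The direction favors CT-P59 if CT-P59 reduces hospitalization or rescue, and the plan assumes the composite is more than twice as frequent on placebo.

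The part due to hospitalization is at most about 0.75–2.25 percentage points. This rests on the Day 28 composite as a proxy and on an assumed 25–75% of affected patients converting. The Day 14 effect is likely smaller, since fewer events occur by then; 36 against 16 patients is not a Day 14 count. Rescue without hospitalization would add an amount that cannot be sized from the documents. If conversions before hospitalization are in fact meant to count, the simulated ratio falls to 1.02–1.05; the SAP does not say that they do. This should be corrected, but no confirmatory claim depends on it.

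**What to change.** In SAP 9.3, give time to negative conversion its own rule:

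- Date the event from the observed RT-qPCR swabs regardless of hospitalization or rescue. At minimum, always count a conversion dated before the hospitalization or rescue.
- Censor patients without conversion at the visit of interest, with Day 14 and Day 28 stated separately. Keep patients who die unconverted as unconverted to that visit.
- Keep two labelled sensitivity analyses: the current rule, and a version in which only antiviral rescue counts as non-conversion.
- Report by arm how many hospitalized or rescued patients count as converted on one negative followed by all missing results.

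Time to NEWS2 of 0 inherits the same rule, so the SAP should also say whether that is intended.

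The cost is SAP wording, settled before unblinding, and reruns of an existing program. The downside is that clearance after antiviral rescue counts as conversion in the main analysis; the sensitivity analyses show how much that matters.
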